8.3.8. Adverse Events of Special Interest

Not applicable.

8.3.8.1. Lack of Efficacy

This Phase 1 study is not designed to investigate the definitive clinical efficacy of PF-07260437.

8.3.9. Medical Device Deficiencies

Not applicable.

8.3.10. Medication Errors

Medication errors may result from the administration or consumption of the study intervention by the wrong participant, or at the wrong time, or at the wrong dosage strength.

Exposures to the study intervention under study may occur in clinical trial settings, such as medication errors.

Safety Event	Recorded on the CRF	Reported on the CT SAE Report Form to Pfizer Safety Within 24 Hours of Awareness
Medication errors	All (regardless of whether associated with an AE)	Only if associated with an SAE

Medication errors include:

- Medication errors involving participant exposure to the study intervention;
- Potential medication errors or uses outside of what is foreseen in the protocol that do or do not involve the study participant.
- The administration of expired study intervention;
- The administration of an incorrect study intervention;
- The administration of an incorrect dosage;
- The administration of study intervention that has undergone temperature excursion from the specified storage range, unless it is determined by the sponsor that the study intervention under question is acceptable for use.

Such medication errors occurring to a study participant are to be captured on the medication error page of the CRF, which is a specific version of the AE page.

In the event of a medication dosing error, the sponsor should be notified within 24 hours.

Whether or not the medication error is accompanied by an AE, as determined by the investigator, the medication error is recorded on the medication error page of the CRF and, if applicable, any associated AE(s), serious and nonserious, are recorded on the AE page of the CRF.

Medication errors should be reported to Pfizer Safety within 24 hours on a CT SAE Report Form **only when associated with an SAE**.

8.4. Pharmacokinetics

Blood samples of approximately 3 mL, to provide a minimum of 1 mL serum, will be collected for measurement of serum concentrations of PF-07260437 as specified in the **SOA**. If CRS is suspected, and if a PK sample is not already scheduled to be taken, a PK sample should also be taken. Instructions for the collection and handling of biological samples will be provided in the laboratory manual or by the sponsor. The actual date and time (24-hour clock time) of each sample will be recorded.

All efforts will be made to obtain the samples at the exact nominal time relative to dosing. Collection of samples within the sampling time window specified in the Pharmacokinetic and

Biomarker Sampling table (see [Section 1.3](#)) will not be captured as a protocol deviation, as long as the exact time of the collection is noted on the source document and the CRF. If a scheduled blood sample collection cannot be completed for any reason, the missed sample time may be re-scheduled with agreement of the clinical investigator, participant, and sponsor.

Samples will be used to evaluate the PK of PF-07260437. Samples collected for analyses of PF-07260437 serum concentration may also be used to evaluate safety or efficacy aspects related to concerns arising during or after the study, for evaluation of the bioanalytical method, or for other internal exploratory purposes.

Genetic analyses will not be performed on these serum samples unless consent for this was included in the informed consent. Participant confidentiality will be maintained.

Samples collected for measurement of serum concentrations of PF-07260437 will be analyzed using a validated analytical method in compliance with applicable SOPs.

The PK samples must be processed and shipped as indicated in the instructions provided to the investigator site to maintain sample integrity. Any deviations from the PK sample handling procedure (eg, sample collection and processing steps, interim storage, or shipping conditions), including any actions taken, must be documented, and reported to the sponsor. On a case-by-case basis, the sponsor may determine as to whether sample integrity has been compromised.

Any changes in the timing or addition of time points for any planned study assessments must be documented and approved by the relevant study team member and then archived in the sponsor and site study files but will not constitute a protocol amendment. The IRB/EC will be informed of any safety issues that require alteration of the safety monitoring scheme or amendment of the ICD.

8.5. Genetics

8.5.1. Specified Genetics

Genetics (specified analyses) are not evaluated in this study.

8.5.2. Retained Research Samples for Genetics

A 4 mL whole blood sample optimized for DNA isolation Prep D1 will be collected according to the [SOA](#), as local regulations and IRBs/ECs allow..

Retained Research Samples may be used for research related to study intervention(s) and cancer study. Genes and other analytes (eg, proteins, RNA, nondrug metabolites) may be studied using the retained samples.

See [Appendix 5](#) for information regarding genetic research. Details on processes for collection and shipment of these samples can be found in the Laboratory Manual.

8.6. Biomarkers

A key element of this study is the evaluation of potential cellular and molecular signatures that could be modified by PF-07260437. The biomarker studies will be used to evaluate the in vivo MoA of PF-07260437, as monotherapy, and potential in combination with other agents, as well as evaluate potential mechanisms of resistance.

Table 12 below summarizes the biomarker assays that include, but are not limited to, those which will be used and the source of the samples. Additional biospecimens collected over the course of participant disease management may be submitted for biomarker analyses. Refer to the [SOA](#) for details pertaining to specific days of sample collection and to the study manual for details of sample preparation. The biomarker sampling schedule may be modified based on emerging PK and PD data.

Table 12. Biomarker Collections and Analyses

Assay	Sample Type
Measurement of B7-H4 expression levels and other tumor and immune biomarkers	Archival and de novo pre-treatment tumor biopsies
Immunophenotyping of blood immune cell subtypes frequency and activation modulation	Whole blood
Measurement of peripheral cytokines and other circulating markers	Serum
Modulation of intra-tumoral target pathway modulation (ie, gene expression signature, cellular and protein changes)	De novo pre-, on-, post-treatment tumor biopsies
Measurement of tumor mutational changes	Plasma pre- and post-treatment
Germline DNA	Whole Blood

Biospecimens collected for PD and other biomarker assessments may include but are not limited to peripheral blood and tumor tissues and may be used to analyze DNA, RNA, proteins, or metabolic biomarkers, for achieving planned biomarker objectives. Refer to the [schedule of activities](#) for sample collection time points and Laboratory Manual for sample processing and shipping. The following biospecimen types are planned to be collected in support of study objectives. Additional biospecimens collected over the course of participant disease management may be submitted for biomarker analyses.

Tumor biospecimens from archival and/de novo biopsies will be used to analyze candidate nucleic acid and protein and cellular biomarkers for their ability to inform those participants who are most likely to benefit from treatment with the study drugs. Biomarkers may include, but are not limited to target expression, nucleic acid analyses, as well as cell types and constituents of the TME. Optional, and/or de novo tumor biopsies obtained during therapy and upon disease progression may be used to help confirm pharmacodynamic effects of treatment and investigate potential acquired mechanisms of resistance (ie, presence of but not

limited to regulatory T cells or myeloid-derived suppressor cells and other immune suppressive cells or proteins).

8.6.1. Tumor Sample Collection for Part 1

All participants in Part 1 must provide an archival FFPE tumor tissue sample (block preferred) at screening. Samples provided should be taken from the most recently conducted available biopsy, preferably within 6 months of start of study treatment, containing sufficient tumor tissue of diagnostic quality and representative of the diagnosed malignancy. Tissue blocks are preferable, but freshly cut paraffin sections are acceptable. Sites should contact sponsor for approval to submit slides and refer to Laboratory manual for instructions on submitting slides. Tumor tissue from cytologic sampling (eg, fine needle aspiration, including FFPE cell pellet material) and bone biopsy specimens are not adequate and should not be submitted.

If the archived sample is older than 12 months, the investigator must contact the sponsor's Medical Monitor to discuss eligibility prior to enrollment.

If an appropriate archival FFPE tumor sample is not available, a de novo fresh FFPE tumor sample should be collected. Each de novo collections (pre-treatment and on-treatment) should attempt to obtain 6 core biopsies, with a minimum of preferably 3 cores. Samples should be obtained in accordance with local institutional practice for tumor biopsies. If a biopsy cannot be performed safely or insufficient tumor biopsy material due to safety risk, the participant may still be eligible. However, such exceptions should be discussed with and approved by the sponsor.

In Part 1, optional de novo pre- and on-treatment tumor biopsies are encouraged for all participants on the trial when participants have accessible lesions. Optional on-treatment tumor biopsies are preferentially collected after the third dose, within 7 days of Cycle 2 Day 15 (C2D15 \pm 7 days). Additional information on tissue collection procedures can be found in the Laboratory/Study Manual.

8.6.2. Tumor Sample Collection for Part 2

In Part 2, archival biopsies should be requested from all participants, in order to establish relationship between target expression and efficacy observations. Archival biopsies should meet the criteria outlined in Section 8.6.1.

De novo pre-treatment biopsies are also requested from all participants, unless not medically feasible, to further establish the relationship between target expression and efficacy observations. If a de novo pre-treatment biopsy is not medically feasible, the sponsor should be contacted for approval before initiating screening activities. For a subset of participants in all cohorts (approximately 5 participants in Part 2A and 2C, and approximately 5 HR+ HER2- BrCa and 5 TNBC participants in Part 2B), mandatory pre-treatment and on-treatment biopsy samples will also be collected in order to confirm the MoA and evaluate potential resistance mechanism during treatment. For all other participants, on-treatment biopsies are optional but encouraged. In Part 2, 20 participants will be enrolled in each

cohort. If 15 participants have been enrolled in Part 2A or Part 2C and <5 paired pre- and on-treatment biopsies have been collected, collections may be made mandatory for the remaining participants and the cohort may be expanded by up to 5 participants to obtain sufficient numbers of paired pre- and on-treatment biopsies. If 5 participants with HR+ HER2- BrCa or TNBC have been enrolled in Part 2B and <5 paired pre- and on-treatment biopsies have been collected, collections may be made mandatory for the remaining participants in each histology and the cohort may be expanded to obtain sufficient numbers of paired pre- and on-treatment biopsies. If a de novo pre-treatment biopsy is not medically feasible, the sponsor should be contacted for approval before initiating screening activities.

For participants with a pre-treatment biopsy, an additional optional biopsy is also encouraged at disease progression to evaluate suspected acquired resistance to therapy. Mandatory de novo tumor collections (pre-treatment and on-treatment) should attempt to obtain 6 core biopsies, with a minimum of preferably 3 cores. Samples should be obtained in accordance with local institutional practice for tumor biopsies. Additional information on tissue collection procedures can be found in the Laboratory Manual.

Mandatory pre-treatment de novo tumor biopsies are to be collected within 28 days of first study treatment dose. On-treatment tumor biopsies are preferably collected after the second dose, within 7 days of Cycle 2 Day 15 (C2D15 \pm 7 days). If on-treatment tumor collection takes place greater than \pm 3 days from C2D15, additional unscheduled blood sample for cytokine and circulating markers and an unscheduled blood sample for T-cell immunophenotyping sample should be collected to match the day of biopsy collection.

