PK blood sampling		A, B, C, D	A, C (IV only)	A, C	A, C	A	A	A, C	A	A	A (Priming only)	A	X	
 • Pre-dose samples: hours before the immediate dose • Post-dose samples: hours after the most recent scheduled dose • If CRS is suspected, additional PK sample should be collected at time of AE occurrence if not already scheduled • IV only: if actual duration of infusion differs from 1 hour, 1-hour point should be adjusted for the sample to be collected at the end of infusion. • See Section 8.4 for additional information.
Immunogenicity Assessments														
Blood samples for ADA and NAb		A, B, C, D											X	
 • From Cycle 4 onwards: collection on Day 1 of every 3 cycles. (C4D1, C7D1, etc.) • See Section 8.7 for additional information.
Pharmacodynamic and Biomarker Samples														

Table 6. PK, Immunogenicity, PD, Biomarker, and Biospecimen Schedule of Assessments – With or Without Priming

Visit Identifier Abbreviations used in this table may be found in Appendix 16	Screening	CYCLE 1 - A CYCLE 2 - B CYCLE 3 - C CYCLE ≥4 - D										EOT	Notes	
		Day 1				Day 2	Day 8	Day 15			Day 16	Day 22		
Hours Before/After Dose		Pre (0)	1 hr	4 hr	8 hr	24 hr	168 hr	Pre (0)	4 hr	8 hr	24 hr	168 hr		
Visit Window		-6 hr	+ 10 min	± 30 min	±1 hr	±3 hr	±24 hr	-6 hr	± 30 min	±1 hr	±3 hr	±24 hr		
Soluble B7-H4 blood sample		A, B, C, D					A	A					X	
 From Cycle 4 onwards: collection on Day 1 of every 3 cycles. (C4D1, C7D1, etc.) See Section 8.6.6 for additional information.
Serum for cytokine and circulating markers (central lab)		A, B	A	A	A	A	A	A	A	A	A	A		
 Refer to Section 8.6.3.
Blood sample for immunophenotyping		A, B				A	A	A			A (Priming only)	A		
 Refer to Section 8.6.4.
Optional or mandatory archival tissue	X													
 Optional if de novo tissue sample is provided. Mandatory if a de novo tissue sample is not provided. Refer to Section 8.6.2 for details.
Mandatory or optional de novo	X							B					(X)	
 (x) = Optional

PFIZER CONFIDENTIAL

CT02-GSOP Oncology Clinical Protocol Template (01 March 2021)

Page 65

Table 6. PK, Immunogenicity, PD, Biomarker, and Biospecimen Schedule of Assessments – With or Without Priming

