6.1.1.2. SC Administration

Qualified and trained investigational site personnel will administer PF-07260437 to participants by SC injection. PF-07260437 will be administered at a flat dose via SC injection Q2W at 28-day cycles (on Day 1 and Day 15) until the participant meets one of the study intervention discontinuation criteria (See [Section 7.1](#)). Participants should have SC injections in the abdomen with preference to the lower quadrants when possible. For participants receiving 2 or more SC injections, PF-07260437 should be administered in 2 or more different quadrants of the abdomen (with preference given to the lower quadrant when possible); 1 or 2 injections per quadrant. The injection can be rotated with each administration for participant comfort. Refer to [Appendix 14](#), for details on administration of multiple injections to the abdomen.

Each injection volume may be up to 2 ml in volume. If an institutional policy sets a maximum volume <2 ml, the number of injections may be increased to ensure that the correct volume is administered. Refer to the IP Manual for specific instructions on the handling and preparation of study treatment.

Refer to [Table 7](#) for required inpatient observation stays following PF-07260437 administration.

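### In Part 2, biopsies taken within 3 days of C2D15 get no matched cytokine or immunophenotyping blood, because the matching rule presumes a C2D15 draw that Table 6 does not schedule

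*Protocol*

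**What the plan says.** Protocol Section 8.6.2 sets the timing for Part 2: "On-treatment tumor biopsies are preferably collected after the second dose, within 7 days of Cycle 2 Day 15". It then gives a matching rule that applies only when the biopsy is more than 3 days either side of C2D15. In that case an "additional unscheduled blood sample for cytokine and circulating markers and an unscheduled blood sample for T-cell immunophenotyping sample should be collected to match the day" on which the tissue is taken.

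Table 6 (Section 1.3.3.1) marks each sample by cycle: A is Cycle 1, B is Cycle 2, C is Cycle 3 and D is Cycle 4 onwards. The on-treatment biopsy has code B in the Day 15 pre-dose column, which is C2D15. The two blood rows that the rule refers to, "Serum for cytokine and circulating markers (central lab") and "Blood sample for immunophenotyping", have code B in the Day 1 pre-dose column and nowhere else. Their Day 15 entries are code A.

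For Part 1, Section 8.6.1 gives the same window with a different dose count: "Optional on-treatment tumor biopsies are preferentially collected after the third dose, within 7 days of Cycle 2 Day 15". It contains no blood-matching rule. On dosing, Section 6.1.1.2 states: "PF-07260437 will be administered at a flat dose via SC injection Q2W at 28-day cycles (on Day 1 and Day 15").

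**The concern.** A rule that adds blood only when the biopsy strays from C2D15 implies that a biopsy near C2D15 is already covered by a scheduled draw. If there is no such draw, the rule works against its own aim: biopsies at the planned time go without matched blood, and those towards the edges of the window receive it.

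At stake is the ability to read tumor T-cell changes beside peripheral cytokines and T-cell activation measured on the same day. Section 4.1 says that the mandatory pairs are meant to confirm the mechanism and to understand pharmacodynamics in the tumor. Pairs are few, at 5 per histology in each cohort, and a blood sample not taken on the day cannot be recovered later.

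**Working it through.** The documents give no figure to reproduce. The check sets the Section 8.6.2 rule beside Table 6 and counts days.

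**Step 1: what Table 6 schedules in Cycle 2.**

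| Table 6 row | Where code B (Cycle 2) appears | Day 15 pre-dose entry |
|---|---|---|
| On-treatment biopsy | Day 15 pre-dose | B |
| Cytokine and circulating markers | Day 1 pre-dose only | A |
| Immunophenotyping | Day 1 pre-dose only | A |
| PK | Day 1 pre-dose only | A, C |
| Soluble B7-H4 | Day 1 pre-dose only | A |

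The cytokine and immunophenotyping rows have no C or D code, so neither assay has a scheduled draw after C2D1. Tables 2 and 4 (Part 1) also show B only at Day 1 for these two assays, which makes a shifted column in the extracted text unlikely.

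**Step 2: convert to study days.** Study day = (cycle − 1) × 28 + day.

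- C2D1 = 28 + 1 = 29; C2D15 = 28 + 15 = 43.
- Permitted window: 43 ± 7 = days 36 to 50, or 50 − 36 + 1 = 15 days.
- No extra blood required: 43 ± 3 = days 40 to 46, or 46 − 40 + 1 = 7 days.

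**Step 3: apply the rule across the window.**

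| Biopsy day | Study day | Days in band | Same-day blood required? | Days since the C2D1 draw |
|---|---|---|---|---|
| C2D8 to C2D11 | 36 to 39 | 4 | Yes | not needed |
| C2D12 to C2D18 | 40 to 46 | 7 | No | 40 − 29 = 11 to 46 − 29 = 17 |
| C2D19 to C2D22 | 47 to 50 | 4 | Yes | not needed |

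The bands sum to 4 + 7 + 4 = 15. A biopsy on C2D15 itself falls 43 − 29 = 14 days after the last scheduled sample.

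**Step 4: how many pairs could be touched.** The mandatory pairs number 5 (Part 2A) + 5 (Part 2C) + 5 + 5 (the two histologies in Part 2B) = 20. Optional on-treatment biopsies in other Part 2 participants follow the same rule.

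**Step 5: dose wording.** Doses fall on study days 1, 15, 29 and 43. Every day in the window (36 to 50) follows at least the third dose, and days 44 to 50 follow the fourth. The window opens 36 − 15 = 21 days after the second dose. The dose count in Section 8.6.1 fits the opening of the window. The count in Section 8.6.2 is literally true of every window day, but it is not the dose that precedes the window.

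**The case against.** The best defence is that little depends on this. Section 3 makes the phenotype and quantity of tumor-infiltrating lymphocytes the secondary tissue endpoint, and Section 9.3.6.1 summarises biopsy markers at baseline and after treatment. Both can be done from tissue alone. Cytokines and blood immunophenotyping are separate exploratory endpoints. The protocol specifies no tissue-to-blood correlation, and the SAP refers exploratory results to a biomarker SAP that is not available here. Section 8.6 also lets the sponsor modify biomarker sampling as data emerge. The point about endpoints stands and limits the size of the problem. The flexibility clause does not cure it: it is discretionary and tells no site to draw C2D15 blood now. Routine safety laboratory tests in Cycle 2 are no substitute for these assays.

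Four stronger readings are tempting, but the documents do not support them:

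- *Only off-schedule participants get matched blood.* C2D8 to C2D11 and C2D19 to C2D22 are permitted days, 8 of the 15, and they do trigger it.
- *The matched dataset will be empty.* That is a worst case, which needs every biopsy to fall within the 7 central days.
- *The plan fails to deliver a matched drug level.* Table 6 has no PK draw at C2D15, but the Section 8.6.2 rule never promises one at any biopsy.
- *The second-dose wording sends sites outside the window.* The sentence states the dose and the C2D15 window together, and every window day is after the second dose. The mixture of three-dose and four-dose biopsies comes from the ±7 days and would remain if the wording were aligned.

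**Conclusion.** The rule and the table are inconsistent, and the rule as written defeats its stated purpose for biopsies on C2D12 to C2D18. Those biopsies get no same-day cytokine, circulating-marker or immunophenotyping sample. The number affected lies between none and all of the 20 mandatory pairs, depending on where sites place the biopsies, and the documents give no basis for a closer estimate.

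The loss is confined to exploratory peripheral pharmacodynamic data. It does not reach the tissue endpoint, the primary safety endpoints or any dosing decision. It is still worth correcting before Part 2 opens, because the protocol itself shows an intent to match blood to biopsy and the correction is small. The different dose counts in Sections 8.6.1 and 8.6.2 are an editorial mismatch.

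The day counts assume nominal visits with no dose delay and the Day 1 and Day 15 schedule. They also assume that no unscheduled draw for suspected cytokine release syndrome (Section 8.6.3) happens to coincide with the biopsy.

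**What to change.** Preferred: in Section 8.6.2, delete the condition on distance from C2D15, so that cytokine/circulating-marker and T-cell immunophenotyping samples are drawn on the day of every Part 2 on-treatment biopsy. Add this to the two rows and the notes of Table 6.

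Alternative: add code B at Day 15 pre-dose for both assays in Table 6 for biopsied participants and keep the 3-day rule. This is weaker. It gives a draw within 3 days of the biopsy at nominal timing, not on the same day, for C2D12 to C2D14 and C2D16 to C2D18.

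Separately, make the dose count in Sections 8.6.1 and 8.6.2 agree for what is the same C2D15 ±7 window. A PK sample at the biopsy (about 3 mL) is an optional addition that the present rule does not call for.

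Cost: two tubes of about 5 mL (Sections 8.6.3 and 8.6.4), so about 10 mL per biopsied participant, for some 20 mandatory pairs plus any optional biopsies. The draw will occasionally fall outside a scheduled dosing visit, but the participant is already attending for the biopsy.
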